23.10. Definition of Peripheral Vascular Intervention

1. Peripheral Vascular Intervention (PVI): Peripheral vascular intervention is a catheter-based or open surgical procedure designed to improve peripheral arterial or venous blood flow or otherwise modify or revise vascular conduits. Procedures may include, but are not limited to, balloon angioplasty, stent placement, thrombectomy, embolectomy, atherectomy, dissection repair, aneurysm exclusion, treatment of dialysis conduits, placement of various devices, intravascular thrombolysis or other pharmacotherapies, and open surgical bypass or revision.

In general, the intention to perform *percutaneous* peripheral vascular intervention is denoted by the insertion of a guide wire into a peripheral artery or vein.

The target vessel(s) and the type of revascularization procedure (e.g., surgical bypass, thrombectomy, endarterectomy, percutaneous angioplasty, stent placement, thromboembolectomy, and thrombolysis) should be specified and recorded. For the sake of simplicity, this definition applies to the extracranial carotid artery and other non-cardiac arteries and veins and excludes the intracranial vessels and lymphatics.

2. **Procedural Success:** In the case of percutaneous intervention for obstructive lesions, procedural success is defined as the achievement of a satisfactory final residual diameter stenosis by angiography at the end of the procedure (and without flow limiting dissection or hemodynamically significant translesional pressure gradient). The specific parameter for final percent residual stenosis is typically between < 30% and < 50%; selection of the appropriate percentage may vary depending upon the specific intervention applied, the vascular territory, and anticipated or desired therapeutic response. Procedural success also implies absence of in-hospital major adverse events (e.g., death, stroke, myocardial infarction, acute onset of limb ischemia, need for urgent/emergent vascular surgery, and other procedure-specific major adverse events). The balloon inflation, stent placement, or other therapeutic intervention may be preceded by use of adjunctive devices (e.g., percutaneous mechanical thrombectomy, directional or rotational atherectomy, laser, and chronic total occlusion crossing device), as predefined in the protocol.
3. **Procedural Status: Non-Elective and Elective:**
 - a. **Non-Elective:** Non-elective procedures include emergent and urgent procedures. A non-elective procedure is a procedure that is performed without delay, because there is clinical consensus that the procedure should occur imminently. Non-elective procedures imply a degree of instability of the patient, urgency of the medical condition, or instability of the threatening lesion.
 - **Emergent:** A procedure that is performed immediately because of the acute nature of the medical condition (e.g., acute limb ischemia, acute aortic dissection), and the increased morbidity or mortality associated with a temporal delay in treatment.

- **Urgent:** An urgent procedure is one that is not emergent but required to be performed on a timely basis (≤ 24 hrs) (e.g., a patient who has been stabilized following initial treatment of acute limb ischemia, and there is clinical consensus that a definitive procedure should occur within the next 24 hours).
- b. Elective:** An elective procedure is one that is scheduled and is performed on a patient with stable disease, or in whom there is no urgency and/or increased morbidity or mortality associated with a planned procedure.
1. **Target Lesion:** A target lesion is any lesion treated or attempted to be treated during the trial procedure with the index device. The target lesion is the treated segment starting 5 mm proximal and ending 5 mm distal to the index device (stent, in most cases).
 2. **Target Vessel:** A target vessel is any vessel (e.g., non-cardiac or non-cerebrovascular vessel) that contains the target lesion treated with the study device. The target vessel includes the target lesion as well as the entire vessel upstream and downstream to the target lesion, including side branches (native vessel).
 3. **Non-Target Lesion:** A non-target lesion is one for which revascularization is not attempted or one in which revascularization is performed using a non-study device.
 4. **Non-Target Vessel:** A non-target vessel is one for which revascularization is not attempted or one in which revascularization is performed using a non-study device.
 5. **Target Vessel, Non-Target Lesion:** Any lesion or revascularization of a lesion in the target vessel other than the target lesion.
 6. **Target Lesion Revascularization (TLR):** Target lesion revascularization is any repeat percutaneous intervention of the target lesions (including 5 mm proximal and distal to the index device) or surgical bypass of the target vessel performed for restenosis or other complication involving the target lesion. In the assessment of TLR, angiograms should be assessed by an angiographic core laboratory (if designated) and made available to the Clinical End Points Committee (CEC) for review.

7. **Target Vessel Revascularization (TVR)**: Target vessel revascularization is any repeat percutaneous intervention or surgical bypass of any segment of the target vessel. In the assessment of TVR, angiograms should be assessed by an angiographic core laboratory (if designated) and made available to the CEC for review.
8. **Clinically-Driven Target Lesion Revascularization**: Clinically-driven target lesion revascularization is a target lesion revascularization prompted by recurrent ipsilateral limb symptoms (intermittent claudication, critical limb ischemia) or objective imaging evidence of target lesion restenosis (i.e., most commonly with duplex ultrasonography). In the assessment of clinically driven TLR based on duplex ultrasonography, ultrasonographic images should be assessed by a duplex ultrasound core laboratory (if designated) and made available to the CEC for review.

23.11. Definition of Any Revascularization Procedure

Any revascularization includes any arterial vascular intervention done to treat ischemia or prevent major ischemic events, including percutaneous or surgical intervention of the coronary, peripheral, or carotid arteries. Aneurysm repairs, dissection repairs, arterial-venous fistula or graft placement or repairs, or renal arterial intervention for hypertension or renal dysfunction are not included.

23.12. Definition of Cardiac Arrhythmia Requiring Hospitalization

An arrhythmia that either results in hospitalization during or within 24 hours of the termination of the last episode for treatment or requires continued hospitalization for treatment, including any one of the following:

1. Atrial arrhythmia – atrial fibrillation, atrial flutter, supraventricular tachycardia that requires cardio-version, drug therapy, or is sustained for greater than 1 minute)
2. Ventricular arrhythmia - Ventricular tachycardia or ventricular fibrillation requiring cardio-version and/or intravenous anti-arrhythmics
3. Bradyarrhythmia - High-level AV block (defined as third-degree AV block or second-degree AV block), junctional or ventricular escape rhythm, or severe sinus bradycardia

(typically with HR < 30 bpm). The bradycardia must require temporary or permanent pacing,

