Beneficial effects in clinical trials have been attributed in part to reducing arrhythmias (Lee 2003; Goel 2002; Calo 2005). The case for an antiarrhythmic effect of O3FAs comes from clinical trials and from animal studies. Clinical trials have shown that the risk of sudden death in patients who have survived myocardial infarction is greatly reduced by inclusion of O3FAs in the diet (Siscovick 2000). Thus it seems that fatal ventricular fibrillation is less likely to occur during sufficient intake of O3FAs. Animal studies support this. Coronary ligation studies in a variety of species (rats, dogs and marmosets) have shown that the incidence of ventricular fibrillation is lower in animals fed a diet rich in O3FAs before ligation (McLennan 1992; Leaf 1996). In isolated cells, the story is similar (Li 1997, Engler 2000; Omura 2001). In neonatal rat cardiac myocytes, EPA prevents the arrhythmogenic action of many interventions, including high external Ca^{2+} and ouabain (Kang 1994). The antiarrhythmic effect is caused by a reduction in electrical excitability caused by partitioning O3FAs into the phospholipid cell membranes of the cardiac myocytes, which modulates membrane ion channels. This is the postulated direct mechanism that refers to the antiarrhythmic effect of O3FAs which inhibits the fast, voltage-dependent sodium current along with the L-type calcium currents. This reduces the action potential of cardiac myocytes, reducing the susceptibility to arrhythmia. These cellular alterations are likely to reduce the severity of ventricular arrhythmias by inhibiting the rapid accumulation of intracellular Ca^{2+} following ischemia. It was also shown in patients with coronary artery disease that long-term treatment with EPA augments both NO-mediated and non-NO-mediated endothelium-dependent forearm vasodilatation (Tagawa 1999).

Another, indirect mechanism refers to the effect of O3FAs on cardiac arrhythmias by modifying the balance of different eicosanoids which are produced as end-products from chain elongation of their parent polyunsaturated fatty acids (Nair 1997). Most investigations of the link between O3FAs and heart disease have demonstrated the competition between AA

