9.2.2. Secondary Efficacy Endpoints

The key secondary efficacy endpoint is:

- The composite of death from CV causes, nonfatal MI, coronary revascularization, unstable angina determined to be caused by myocardial ischemia by invasive/non-invasive testing and requiring emergent hospitalization, nonfatal stroke, or peripheral CVD requiring intervention, angioplasty, bypass surgery, or aneurysm repair.

Other secondary efficacy endpoints are as follows (to be tested in said order):

- The composite of total mortality, nonfatal MI, or nonfatal stroke;
- The composite of death from CV causes, nonfatal MI, coronary revascularization, unstable angina determined to be caused by myocardial ischemia by invasive/non-invasive testing and requiring emergent hospitalization, peripheral CVD requiring intervention, or cardiac arrhythmia requiring hospitalization;
- The composite of death from CV causes, nonfatal MI, coronary revascularization, or unstable angina determined to be caused by myocardial ischemia by invasive/non-invasive testing and requiring emergent hospitalization;
- The composite of death from CV causes or nonfatal MI;
- Total mortality;
- Fatal and nonfatal MI (including silent MI);
- Coronary Revascularization;
- Hospitalization for unstable angina determined to be caused by myocardial ischemia by invasive/non-invasive testing ;
- Fatal and nonfatal stroke.

For the secondary endpoints that count a single event, the first occurrence of this type of event will be counted in each patient. For secondary endpoints that are composites of two or more types of events, the first occurrence of any of the event types included in the composite will be counted in each patient.

9.2.3. Tertiary Efficacy Endpoints:

- The second, third, fourth, and fifth major CV event of the primary composite endpoint. The type of (nonfatal) events may occur in any order.
- Primary endpoint in subset of patients with diabetes mellitus;
- Primary endpoint in subset of patients with metabolic syndrome;
- New CHF, new CHF leading to hospitalization, transient ischemic attack, amputation for CVD and carotid revascularization;
- Elective coronary revascularization and emergent coronary revascularization;
- New onset diabetes;
- Fasting TG, TC, LDL-C, HDL-C, non-HDL-C, VLDL-C, apo B, hs-CRP, and hsTnT: effect of baseline and on-treatment change of biomarkers on primary and key secondary endpoints;

- CV mortality;
- Cardiac Arrhythmias requiring hospitalization;
- Cardiac Arrest;

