- To explore the effect of AMR101 on weight and waist circumference.

For the tertiary endpoints that count a single event, the first occurrence of this type of event will be counted in each patient. For tertiary endpoints that are composites of two or more types of events, the first occurrence of any of the event types included in the composite will be counted in each patient (except when stated otherwise, for the second, third, fourth, and fifth major CV event).

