10.2.1. Serious Adverse Events

A serious adverse event (SAE) is defined as an adverse event that meets **any** of the following criteria:

- Results in death
- Is life-threatening- Note: The term “life-threatening” in the definition of “serious” refers to an event in which the patient was at risk of death at the time of the event. It does not refer to an event, which hypothetically might have caused death, if it were more severe.
- Requires hospitalization or prolongation of existing hospitalization- Note: In general, hospitalization for treatment of a pre-existing condition(s) that did not worsen from baseline is not considered adverse events and should not be reported as SAEs.
- Results in disability/incapacity
- Is a congenital anomaly/birth defect;
- Is an important medical event- Note: Important medical events that may not result in death, be life threatening, or require hospitalization may be considered an SAE when, based upon appropriate medical judgment, they may jeopardize the patient and may require medical or surgical intervention to prevent one of the outcomes listed above. Examples of such medical events include allergic bronchospasm requiring intensive treatment in an emergency room or at home, blood dyscrasias or convulsions that do not result in inpatient hospitalizations, or the development of drug dependency.

By design of this study SAEs that are endpoint events will only be recorded for the endpoint determination and not captured as SAEs. The intention is that the endpoint events are not reported to IRBs as SAEs, unless the IRB requires that these are reported. Investigators should specifically inform their institution/IRB of this plan and confirm whether or not they want the endpoint events reported. By agreement with the US FDA, these endpoints will also not be reported to the US FDA as SAEs; rather they will be reported as endpoint events. Following adjudication if the event is determined to not meet the criteria for an event, the event will be evaluated as an SAE beginning with that day as Day 0.

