12.2.5. Analysis of Safety

All analyses of safety will be conducted on the safety population, which is defined as all randomized patients who receive at least one dose of study drug. The safety assessment will be based on the frequency of adverse events, physical exams, vital signs and safety laboratory tests.

Adverse events with new onset during the study between the initiation of study drug and 30 days after the last dose of study drug for each patient will be considered treatment-emergent (TEAEs). This will include any AE with onset prior to initiation of study drug and increased severity after the treatment initiation.

Treatment-emergent adverse events will be summarized by system organ class and preferred term, and by treatment. This will include overall incidence rates (regardless of severity and relationship to study drug), and incidence rates for moderate or severe adverse events. A summary of SAEs and adverse events leading to early discontinuation from the study will be presented through data listings.

Safety laboratory tests and vital signs will be summarized by post-treatment change from baseline for each of the parameters using descriptive statistics by treatment group. Those patients with significant laboratory abnormalities will be identified in data listings. Additional safety parameters will be summarized in data listings.

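### Confirmed hospitalized atrial fibrillation appears only inside a pooled arrhythmia endpoint, and in neither the adverse-event tables nor an analysis of its own

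*Combined protocol and SAP*

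**What the plan says.** All references are to Amendment 1 (16 May 2013) unless stated.

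- **Definition.** Appendix B 23.12 covers an arrhythmia that leads to admission or "requires continued hospitalization for treatment, including any one of the following". Three classes follow. The atrial class groups "atrial fibrillation, atrial flutter, supraventricular tachycardia that requires cardio-version, drug therapy" and similar criteria. The other two are ventricular tachycardia or fibrillation needing cardioversion or intravenous drugs, and bradyarrhythmia needing pacing.
- **Use.** The event is a stand-alone tertiary endpoint in 9.2.3, "Cardiac Arrhythmias requiring hospitalization". It is also a component of one secondary composite in 9.2.2, which ends "peripheral CVD requiring intervention, or cardiac arrhythmia requiring hospitalization".
- **Counting and analysis.** Section 9.2.3 states: "For the tertiary endpoints that count a single event, the first occurrence of this type of event will be counted in each patient". Section 12.2.4.4 analyses tertiary event endpoints in the same way as the secondary ones, by arm and without multiplicity adjustment. It gives no split by rhythm.
- **SAE capture.** Section 10.2.1 says that "SAEs that are endpoint events will only be recorded for the endpoint determination and not captured as SAEs". Events that fail adjudication return to SAE evaluation. The 2011 protocol limited the exemption to primary endpoint events; Amendment 1 removed that limit.
- **Safety analysis.** Section 12.2.5 states: "The safety assessment will be based on the frequency of adverse events, physical exams, vital signs and safety laboratory tests". Treatment-emergent events are tabulated by preferred term and treatment, and SAEs are presented in listings.
- **Rationale.** Section 1.5 invokes a rhythm effect: "Beneficial effects in clinical trials have been attributed in part to reducing arrhythmias". The argument there is mainly about ventricular fibrillation.

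**The concern.** A rhythm effect is part of the stated rationale, so a reader of the results will want to know what happened to each kind of arrhythmia. The plan answers only for the pool. The SAE exemption then removes confirmed arrhythmia hospitalizations from the safety tables, where AF would otherwise be visible under its preferred term. An AF row in those tables would hold the milder or unconfirmed cases and omit the confirmed admissions.

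At stake is whether a real difference in AF, in either direction, could be read from the planned outputs. The primary and key secondary endpoints are not affected.

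**Working it through.** **Step 1. Follow each kind of AF case through the plan.**

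| AF case | Where it is recorded | Planned by-arm display |
|---|---|---|
| Not hospitalized | Adverse event | Preferred-term table (12.2.5) |
| Hospitalized, fails adjudication | Returned to SAE handling (10.2.1) | Preferred-term table; SAE listing |
| Hospitalized, confirmed, patient's first qualifying arrhythmia | Endpoint data only | Inside the pool (9.2.3) and one composite (9.2.2) |
| Hospitalized, confirmed, after another qualifying arrhythmia | Endpoint data only | None as a new event, by the first-event rule |

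No specified output adds these rows together or shows the third row on its own. The last two rows assume that the exemption covers arrhythmia hospitalization. That is the natural reading, because 10.2.1 does not qualify the term endpoint events, 5.3 sends secondary outcome events for adjudication, and arrhythmia hospitalization is a component of a secondary composite. The text does not say so outright.

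**Step 2. Size of the dilution.** The documents give no rate or power for any arrhythmia, so there is no stated figure to reproduce. Inputs:

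- 3995 patients per arm (section 3.6) and a two-sided 5% level (synopsis), hence 1.96.
- Assumed 4-year placebo risks: atrial 2.0%, ventricular 1.0%, brady 0.8%.
- Assumed atrial hazard ratio: 1.5.

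For each class, d0 = 3995p and d1 = 3995[1 − (1 − p)^HR]. Pooled counts are sums over classes, ignoring patients with more than one class. Then R = d1/d0, z = ln(R) × √(d0·d1/(d0 + d1)), and power = Φ(|z| − 1.96).

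Atrial class alone: d0 = 3995 × 0.02 = 79.9 and d1 = 3995 × (1 − 0.98^1.5) = 119.2. R = 1.49, and z = 0.400 × √(79.9 × 119.2/199.1) = 0.400 × 6.92 = 2.77. Power = Φ(0.81) = 79%.

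The other classes have 39.95 ventricular and 31.96 brady events on placebo. At a hazard ratio of 0.7 these become 28.0 and 22.4.

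| Analysis | Placebo v drug events | R | z | Power |
|---|---|---|---|---|
| Atrial alone | 79.9 v 119.2 | 1.49 | 2.77 | 79% |
| Pool, other classes unchanged | 151.8 v 191.2 | 1.26 | 2.12 | 56% |
| Pool, ventricular HR 0.7, brady 1.0 | 151.8 v 179.2 | 1.18 | 1.50 | 32% |
| Pool, ventricular and brady both 0.7 | 151.8 v 169.7 | 1.12 | 0.99 | 17% |

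**Step 3. Range for dilution alone (other classes unchanged), same formulas.**

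- Low corner, atrial risk 1.5% and HR 1.3: atrial 59.9 v 77.7, z = 1.51, power 33%. Pool 131.8 v 149.6, z = 1.06, power 18%.
- High corner, atrial risk 3.0% and HR 1.5: atrial 119.9 v 178.4, z = 3.37, power 92%. Pool 191.8 v 250.3, z = 2.78, power 79%.

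**Step 4. Complete offset.** Take placebo risks of 2% for atrial and 2% for all other arrhythmias, with relative risks of 1.5 and 0.5. Atrial events go from 80 to 120 and the others from 80 to 40, so the pool is 160 v 160. This shows that full cancellation is possible; it needs the other classes to halve.

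**The case against.** Much of the case on the other side is sound.

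- **A reader might infer that AF is never compared by arm.** That goes too far. The pool is compared by arm with time-to-event methods, and AF outside the endpoint is tabulated by preferred term and treatment. The gap is confined to confirmed hospitalized cases.
- **A reader might infer that the pool is the only arrhythmia endpoint.** It is not. Cardiac arrest is a separate tertiary endpoint (9.2.3, defined in 23.13), and deaths attributed to an identified arrhythmia count as CV death.
- **A reader might infer that ECG findings go unreported.** Section 12.2.5 leaves ECGs out of its stated basis, but 10.1 names them as a safety assessment and 12.2.5 sends additional safety parameters to listings. That is thin reporting, but it is not silence.
- **Cancellation has little support in the documents.** Section 1.5 argues for less fatal ventricular fibrillation, which would mostly be counted as cardiac arrest or CV death, outside the pool. Nothing there predicts a rise in AF; one source cited for the rhythm effect is, by its title, a trial of preventing AF after bypass surgery. No benefit on bradyarrhythmia is proposed, so the 17% row is the least supported.
- **Standing of the endpoint.** It is tertiary and unadjusted, the DMC reviews safety during the trial, and class tables could be produced later from adjudication data.

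These points narrow the concern to dilution and to an incomplete AF table. They do not remove it: no planned output shows the missing cases, and a split chosen after unblinding would be post hoc. The separate SAP, the CEC charter and the body of Amendment 2 (July 2016) are not in the text available, so a rhythm-specific analysis there cannot be excluded.

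**Conclusion.** The concern holds in a limited form. Under Amendment 1, confirmed hospitalized AF or flutter is not shown by arm on its own and is absent from the AE and SAE tables, so the most serious AF is separated from the rest. That follows from the definitions and reporting rules and does not depend on any assumed rate. It does depend on reading arrhythmia hospitalization as one of the exempt endpoint events.

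The size is illustrative. With the assumed risks and an atrial hazard ratio of 1.5, pooling lowers power from about 79% to 56% by dilution alone. Offsetting movement in the other classes would lower it further, to 32% or 17%, but the documents give little reason to expect such movement. They also give no reason to conclude that the drug raises AF, and this point makes no such claim. It is a reporting gap worth closing because closing it is cheap.

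**What to change.** Make three changes before unblinding.

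1. **Section 12.2.4.4.** Report adjudicated arrhythmia hospitalizations by arm, with hazard ratio and confidence interval, for each of the three 23.12 classes, counting the first event within each class. Show AF/flutter separately within the atrial class. Keep the pooled endpoint as it is.
2. **Section 12.2.5.** Add one by-arm safety table of AF/flutter that combines adjudicated endpoint events with AE- and SAE-reported cases and counts each patient once. State its time window, because treatment-emergent events stop 30 days after the last dose while endpoint events run to the study end date.
3. **Section 10.2.1.** State whether arrhythmia hospitalization is among the exempt endpoint events.

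If the separate SAP or Amendment 2 already contains the first two, a cross-reference is enough. The cost is a few sentences and two tables. No new procedure is needed, since adjudication under 23.12 already requires the class to be identified. No alpha is spent, because tertiary analyses are unadjusted. The downside is a few more descriptive comparisons, which should be labelled as such.
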